The USFDA licensed 23-valent pneumococcal polysaccharide vaccine covers about 90% of circulating serotypes in Bangladesh (9). It produces high levels of antibody responses in adults (12). A recent study in Bangladesh showed that maternal immunization with the 23-valent polysaccharide pneumococcal vaccine, was safe and immunogenic and protective levels of antibodies (>0.15µg/mL) were observed in the infants' blood up to 22 weeks of age (13). Maternally transferred antibodies play an important role in infant protection, but the antibodies are short lived and may not fully cover the period of high risk. Maternal immunization does not produce impaired responses either with maternal anti-tetanus toxoid (TT) (a protein antigen) or with other polysaccharides as *H. influenzae* B (Hib) in infants (14). This may also induce the effect of priming in the newborn.

Vaccine efficacy depends on the prevalence of the serotypes in the vaccine, the age at which the children become immuno-competent to the predominant serotype, and the naturally acquired immunological response of the children to the important serotypes at the time of immunization (15). In developing countries, the serotypes that cause invasive disease are more likely to be ones that evoke a good immune to immunization in young children (16). Polysaccharide vaccines co-valently linked to a carrier protein are immunogenic in young infants from an early age(15). Clinical trials of the 2,5,7 & 9- valent glycoprotein conjugate pneumococcal vaccine have been conducted in young children both in developing and in developed countries and found to be safe and immunogenic when given along with routine immunization

(17-23). The serotypes in the 7 –valent CRM $_{197}$ product would cover \sim 60% of circulating serotypes here (24).

The proposal is to conduct a prospective randomized, blinded, controlled comparative trial of safety and immunogenicity of 2 US FDA licensed pneumococcal vaccines. Women will be immunized around 32 weeks gestation and infants at birth. To-date no studies have examined the immunogenicity and safety of the conjugate pneumococcal vaccine with maternal immunization.. Globally early infant deaths remain a significant problem, which cannot be addressed with current EPI strategies, even with new vaccines. This project builds on results of a previous study and will build capacity for vaccine evaluation in Bangladesh.

RESEARCH DESIGN AND METHODS:

Study Design:

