A randomized double-blind controlled immunogenicity trial will be conducted in Dhaka in collaboration with private and public facilities providing maternity health care services. In this study mothers will be randomized to receive either the pneumococcal (study) or the meningococcal (control) vaccine All infants will receive the glycoprotein conjugate pneumococcal vaccine.

Setting and Population:

This trial will be carried out in Dhaka, in collaboration with three private and public facilities providing maternity health care services. Pregnant women belonging to the middle-class come to these clinics for ante-natal care and delivery. Healthy pregnant women in the third trimester and their infants will be enrolled after signing informed consent forms. The study population will be pregnant women residing in Dhaka, Bangladesh. Our obstetrical co-investigators have helped us conduct our earlier studies with 180 women. They will again inform their registered patients of the purpose and of the trial, and refer them to our project staff assigned to that clinic. Project staff will provide a detailed explanation of the purpose, procedure, risk and benefits of the trial, answer any questions and then obtain signed informed consent of participation. Assignment to study groups will be instituted as soon as the mother gives concurrence to enroll into the study.

Selection criteria:

Inclusion criteria:

- 1. Women in third trimester of pregnancy with normal medical and obstetric history and physical examination and aged >15 and <40.
- 2. Women who plan to deliver in Dhaka and who plan to remain in Dhaka for the next 12 months.

Exclusion criteria:

- 1. Women with systemic disease as diabetes, hypertension, etc.
- 2. Women with known history of previous complicated pregnancy.
- 3. Women with previous history of preterm delivery and repeated abortions.
- 4. Women with previous history of birth with congenital anomalies.
- 5. Women with hypersensitivity reactions to vaccination.
- 6. Women with receipt of pneumococcal or meningococcal vaccine in last 3 years.

Study Procedure:

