Data regarding demographic and socio-economic characteristics of the subjects will be recorded on the enrollment form. These data will include maternal age, height, years of education, gravidity, parity, date of the last menstrual period, number of adults in household, number of children in household, and father's years of education.

Immunization procedures

- A. Immunization of mothers: The study vaccines will be administered intramuscularly in the deltoid region of the left arm of enrolled mothers, and all mothers will simultaneously receive tetanus toxoid vaccine in the right arm, as recommended by the Government of Bangladesh EPI program.
- B. Immunization of infants: Infants will be assigned to the same study group as their mother, (see Appendix 1). All infants of enrolled mothers will receive the study vaccines at 6, 10 and 14 weeks of age, according to the schedule for their assigned group. At these routine immunization visits they

will simultaneously receive their standard immunizations, which consists of BCG, oral polio vaccine and DPT vaccine. The DPT vaccine will be administered in the left antero-lateral thigh.

C. Post Immunization Monitoring and Procedures: All mothers will be asked to wait in the health facility for 1-2 hours after immunization to monitor immediate side effects. Each enrolled mother will be given a questionnaire regarding possible local and systemic side effects at 24, 48, 72 hours after immunization. Subjects will have contact phone numbers of study team members and will report any reactions to the team. Every home will be visited at 72 hours to collect the reaction data. Data on the pregnancy and delivery will be obtained on all women. Data regarding illness during the pregnancy, the outcome of the delivery, estimated gestational age of the infant determined by the Ballard method (26) at delivery, the complications of delivery, birth weight, and neonatal illnesses will be recorded within 24 hours of delivery. Infants will be retained at the immunization clinic and observed for 1-2 hours after every immunization dose. Families will fill in reaction cards for 72 hours for fever and local and systemic reactions following each dose of vaccine. Study staff will visit the mothers and infants at home to collect information and nasopharyngeal specimens. Routine medical care and routine immunization will be provided for the infant at ICDDR,B clinics during the period of the study.

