In order to determine the success of the randomization procedure, the following variables of the mothers and infants will be compared to determine if the means or proportions are significantly different between the groups: maternal age, height, education, and parity, household size, gestational age at immunization, gestational age at delivery, immunization-birth delivery, birth weight, percent of infants with birth weight less than 2.5 kg, and less than 37 weeks gestation. The geometric mean pneumococcal antibody titers before immunization and at the time of delivery will be compared between mothers in the study groups, by ANOVA. Similarly, the infants' antibody titers to pneumococcal polysaccharide, diphtheria toxoid and tetanus toxoid will be compared between the three study groups in cord, 6 week and 18 week specimens by ANOVA test. The groups will be compared with respect to key characteristics to assess randomization. Proportions with adverse events and proportions seroconverting will be compared using chi-square tests.

We will compare the final infant pneumococcal antibody GMT between study group 1 and 2 to assess the effect of passive antibody on the filial antibody response to three doses of glycoprotein conjugate pneumococcal vaccine.

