
SUMMARY OF ANALYSES

Objectives	Variables	Analysis
Primary: 1a	antibody titer:	t-test, chi square
Immunogenicity	GMT, $\% > 0.15$, $1 \mu g/ml$	regression
Primary: 1b Safety	% reaction rates	chi square
Secondary: 2	cord, final antibody:	correlation
Maternal-filial	GMT, % >0.15, 1 μg/ml	coefficient
Secondary: 3	cord, final antibody; GMT;	means,
EPI schedule	GMT, % >0.15, 1 μg/ml	proportions
Secondary: 4	cord, final antibody; GMT;	chi square,
NP colonization	% colonization rates	regression

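### Five of the 11 variables tested to judge whether randomization worked arise after maternal vaccination, so they cannot answer that question and need a stated purpose of their own

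*Protocol*

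**What the plan says.** The Data analysis section gives the purpose of the comparison: "In order to determine the success of the randomization procedure, the following variables of the mothers and infants will be compared". It gives the method as a significance check: "to determine if the means or proportions are significantly different between the groups". The list that follows has two parts:

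- six variables settled by the time of vaccination: "maternal age, height, education, and parity, household size, gestational age at immunization";
- five settled later: "gestational age at delivery, immunization-birth delivery, birth weight, percent of infants with birth weight less than 2.5 kg, and less than 37 weeks gestation". I read the second item as the interval from immunization to birth, and the last as the percent born before 37 weeks.

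The same paragraph later repeats that group characteristics are compared to assess randomization. It also says that proportions with adverse events will be compared by chi-square test, without naming any event. In Appendix 2 the only variable in the safety row (Primary 1b) is the percentage for "reaction rates".

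**The concern.** A check on randomization has to use variables that the assigned treatment could not have changed. Birth weight and length of gestation do not meet that condition in a trial that vaccinates women during pregnancy. If the arms differ on them, the difference may be chance, an allocation problem or an effect of the vaccine.

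What is at stake is the meaning of such a difference. The Background describes the trial as comparing the safety and immunogenicity of two licensed pneumococcal vaccines, and one of these is the polysaccharide vaccine given to the mothers. Fewer or more small or preterm infants in one arm would matter to that aim. The protocol instead presents the comparison as a test of the allocation procedure.

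**Working it through.** The protocol has no figure to reproduce on this point. The check is the time order of events.

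**Step 1: assignment.** Setting and Population: "Assignment to study groups will be instituted as soon as the mother gives concurrence to enroll into the study".

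**Step 2: vaccination.** Background: "Women will be immunized around 32 weeks gestation". Appendix 1 also places the maternal vaccine at 32 weeks.

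**Step 3: birth data.** Immunization procedures, item C, which covers monitoring after immunization: "birth weight, and neonatal illnesses will be recorded within 24 hours of delivery". Gestational age by the Ballard method is recorded at the same stage.

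**Step 4: sort the 11 variables against that order.**

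| Variable | Settled before the vaccine can act? |
|---|---|
| Maternal age | Yes |
| Maternal height | Yes |
| Education | Yes |
| Parity | Yes |
| Household size | Yes |
| Gestational age at immunization | Yes |
| Gestational age at delivery | No |
| Immunization-to-birth interval | No |
| Birth weight | No |
| Percent under 2.5 kg | No |
| Percent under 37 weeks | No |

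Six precede any vaccine effect and five do not (6 + 5 = 11). With vaccination at about 32 weeks, the 37-week threshold is still about 37 − 32 = 5 weeks away, so preterm status is open for nearly every woman when she is vaccinated.

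**Step 5: look for another between-arm purpose.**

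- The safety row of Appendix 2 contains reaction rates only.
- The adverse-event comparison in Data analysis names no birth outcome. Mean birth weight and mean gestational age are in any case not proportions.
- The multivariable regression uses birth weight and immunization interval as predictors of titer, not as results to be compared between arms.

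No passage supplies one.

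**Step 6: what the birth outcomes could show if reported as arm differences.** Planned enrollment is 63 ÷ 0.7 = 90 per group. The protocol gives no rate of low birth weight, so I assume 10% to 30% in both arms. The 95% half-width for a difference in proportions is 1.96 × √(2p(1 − p)/90):

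- p = 0.10: 1.96 × √(0.18/90) = 8.8 percentage points
- p = 0.20: 1.96 × √(0.32/90) = 11.7 points
- p = 0.30: 1.96 × √(0.42/90) = 13.4 points

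These widths describe precision and do not measure the defect. They do show why an interval is more useful here than a significance test: a non-significant result would leave sizeable differences open.

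**The case against.** The best case for the protocol is that the comparison itself is sound and would be visible. Birth weight and prematurity will be compared by arm, the data are collected alongside side-effect data, adverse events are compared by chi-square test, and the monitoring committee described under Ethical issues receives vaccine reactions and other data. Detailed safety tables can be left to a statistical analysis plan. All of this is true. It limits the consequence, but it does not correct the purpose that the protocol expressly assigns to these five variables. That is a statement made wrongly, not an omission.

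Several stronger readings are tempting and are not supported:

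- *The plan would dismiss a harm signal as chance imbalance.* A reader might infer this, but the protocol gives only a purpose. It states no rule for interpreting a significant difference and no action to follow.
- *The birth outcomes have no safety role at all.* The general references to adverse events and to other data for the committee leave room for one. The accurate statement is that none is named.
- *The outcomes belong under Primary 1b.* Primary objective 1 concerns the conjugate vaccine given to infants, whose first dose is at 6 weeks in Study Procedure and Appendix 1. Birth weight and gestation are settled before then and cannot measure that objective.
- *Using birth weight in the regression hides an arm difference in birth weight.* That model explains titers. It neither removes nor relabels a difference in birth weight, and is a separate matter.
- *Eleven tests at 5% give a 43% chance of a false alarm* (1 − 0.95^11 = 0.43). This is general multiplicity: the six legitimate variables alone give 1 − 0.95^6 = 0.26. It also assumes independence, which fails because several of the variables share a measurement, and the protocol sets no alpha for these tests.

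Both arms receive a vaccine, so any arm difference would be pneumococcal relative to meningococcal vaccine. That affects how a safety result is worded, but it does not make the difference evidence about randomization.

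**Conclusion.** The point holds. Five of the 11 variables listed as a check on randomization arise after assignment and maternal vaccination, and cannot serve that purpose. This rests on the protocol's own time order and on reading the immunization-birth item as an interval; no numerical assumption is needed. The protocol names no other between-arm purpose for the five.

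The consequence is limited to interpretation. The comparison of final infant titers, the 63 evaluable per group and the 90 enrolled per group are unaffected. The change is still worth making, because it settles in advance how a difference in birth outcomes is to be understood in a trial that vaccinates pregnant women and describes itself as comparing vaccine safety.

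**What to change.** In Data analysis:

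- Limit the randomization check to maternal age, height, education, parity, household size, gestational age at immunization and pre-vaccination maternal titers.
- Show these by arm descriptively, without significance tests.
- Describe the immunization-to-birth interval by arm as a post-randomization variable, not as a balance check.

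In Appendix 2:

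- Add a separate maternal-vaccine safety line, apart from Primary 1b.
- Under it, report gestational age at delivery, birth weight, percent under 2.5 kg and percent under 37 weeks as arm differences with 95% confidence intervals.

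The protocol already collects these data, so the cost is wording in two places. The one thing to accept is that the intervals will be wide: about 9 to 13 percentage points either side for percent under 2.5 kg, at the assumed rates. The safety line should therefore be presented as estimation, and a non-significant difference should not be reported as showing that the arms are alike.

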1. To assess whether the presence of maternally derived antibody to pneumococcal polysaccharide (or to the carrier protein) influences the immunogenicity and safety of glycoprotein conjugate pneumococcal vaccine when given to infants during routine immunization.

Secondary Objectives

- 1. To assess the effect of maternally-acquired polysaccharide-specific antibodies on the filial antibody response to glycoprotein conjugate pneumococcal vaccine.
- 2. To assess the effect of maternally-acquired carrier protein-specific antibodies on the filial antibody response to glycoprotein conjugate pneumococcal vaccine, and to active immunization with the carrier protein.
- 3. To determine the IgG antibody responses to conjugate pneumococcal vaccine when given at the standard EPI schedule to Bangladesh infants.
- 4. To assess the effect of specific serum IgG antibody acquired through maternal or infant immunization and of breast milk antibody on acquisition and nasopharyngeal carriage of pneumococci.

Background of the Project including Preliminary Observations

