The primary outcome measures are the infant serum IgG antibody titers to specific capsular pneumococcal polysaccharide, and to the protein carrier moiety of the pneumococcal conjugate vaccine. These data will be generated on coded specimens by the laboratory and reported as microgram per ml for each subject. The comparisons of interest are of the antibody concentrations at birth, which represents passively acquired maternal antibody; and the antibody concentrations after 3 doses of immunization at 18 weeks of age, which represent the active filial antibody response.

Sample size estimate

In order to estimate the sample size required to answer the primary research questions posed in the objectives of this proposal, we used standard sample size formulae and pneumococcal antibody geometric mean and standard deviation data from our studies of the 5 valent Praxis glycoprotein conjugate pneumococcal vaccine given to US infants at 2, 4 and 6 months of age (table 2 below).

Table 1 ANTIBODY MEAN AND SD DATA^{a)}

serotype	N	IgG GMT	mean log	std. dev. of logs	
19F	43	3.6 μg/ml	0.55882	0.605756	
6B	45	2.3 μg/ml	0.36080	0.767809	

^{a)}values are for sera collected at 7 months of age, after 3 doses given at 2, 4 and 6 months of age to US infants

Table 2 utilizes the data in table 1 to show the number of subjects per group which are required to detect the specified differences between the antibody GMTs of groups 1 and 2. Since one goal of the project is to determine if a study group 2 has a lower antibody titer than group 1, a one-sided test of significance is appropriate, however, a 2-sided test allows full examination of the relationships.. A sample size of 63 in each group will allow us to detect a difference of 50% in the final geometric mean titers.

Table 2 SAMPLE SIZE ESTIMATES

group GMT (μg/ml)		Dif	Difference			Number each in group a)		
_ A	B	%	Fold		1 sided	2 sided		
1.8	3.6	-50%	0.5		50	63		
2.5	3.6	-30%	0.7		185	235		
2.7	3.6	-25%	0.75		285	362		
2.9	3.6	-20%	0.80		445	565		

 $^{^{}a)}$ assuming alpha = 0.05, beta = 0.20, power = 80%.

We had 79% rate of completion in our previous study in Dhaka. If 30% of enrolled subjects do not complete the study, $(63 \div 0.7 =)$ 90 subjects will need to be enrolled in each group, for a project total of 180 mother-infant pairs. (Appendix 3)

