Antibody assay validity and variability: Because antibody titers are the principal outcomes of this studies, we have instituted procedures to ensure validity and to reduce the variability of antibody assays. The ELISA for pneumococcal antibody has been standardized using the CDC/WHO standard assay procedures and FDA reference serum by [name] at Johns Hopkins University. Interassay variability is now assessed by running a local control serum (89-1C) on each plate to measure day to day variations. During a recent study of pneumococcal immunization of adults with and without HIV infection the co-efficients of variation for serotypes 6B, 14, 18C, 19F, and 23F were 30%, 12%, 11%, 12%, 16%, respectively. These values were typical for variation as reported by other centers, including the observation that type 6B has greater variability than the remaining serotypes. The laboratory will receive the serum coded and thus they will remain blinded to the code assignments.

Data analysis (see appendix 2)

Sera with undetectable antibody will be assigned half the lower limit of detection for the purposes of calculating means. Because the distributions of antibody titers and of the increases in titer (post-immunization antibody level divided by pre-immunization antibody level) are likely to be positively skewed, the values will be log-transformed to approximate a normal distribution for statistical analyses. The antilogarithms of the means of the log-transformed values will be reported as geometric mean titers (GMT) or as geometric mean increases. Continuous variables will be compared between groups by two-sided T-test or Mann-Whitney U test within groups by the paired T-test, and associations of continuous variables will be assessed by Pearson's correlation coefficient or the Spearman rank correlation test. The Chi Square or Fisher's exact test will be used to compare proportions between groups.

The gestational age of the infants will be estimated by two methods. The mothers will be asked the date of the first day of their last menstrual period, from which we will calculate the duration of the gestation period. In addition, each child will be examined within 48 hours of birth using the method of Ballard to assess the neuromuscular and physical maturity of the infant (25). The Ballard technique assigns a score for neuromuscular and physical maturation and allows an estimation of gestational age.

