The study protocol has been reviewed and approved by the Research and Ethical Review Committees of the ICDDR,B in Dhaka, Bangladesh, and will be reviewed by the Joint Committee for Clinical Investigation of Johns Hopkins Hospital in Baltimore, Maryland.

A data safety and monitoring committee composed of three Bangladeshi physicians not involved in the study will be constituted. The members of the committee will be provided with vaccine reaction and other data by the Principal Investigator periodically during the study, and will communicate by fax and phone with each other and with the PI and Co-PI. These procedures allowed timely review and feedback regarding data and possible safety issues in our previous study in Dhaka.

Tentative Time schedule

We estimate that it will require up to 24 months (2 years) to carry out this study. Our estimate for each activity in the table below is based on our experience with the previous study of maternal immunization. The dates given are subject to project approval at ICDDR,B and JHU, MOU between the two institutions and transfer of funds to ICDDR,B.

Activ	vity	Duration	Sample Dates *
1.	Local project approvals, hiring of field staff	2 months	06/02 * 07/02
2.	Recruitment of subjects	7 months	08/02 - 02/03
3.	Follow up of last infants	6 months	10/02 - 03/03
4.	Laboratory assays, data analysis	9 months	04/03 - 12/03
5.	Report and publication writing	4 months	01/04 - 04/04

Policy Implications:

The results of this enhancement of a planned study will provide a direct comparison of infant immunization strategy with or without maternal immunization. Although a number of strategies have been recommended, a direct comparison of safety and immunogenicity is needed to allow planning for further studies. The expected impact is additional safety and immunologic information on the strategies proposed by WHO to reduce early infant mortality from pneumococcal disease. The results of this study will allow planning for further assessment of that strategy which appears to be the most effective.

Collaborative Arrangement

This is a collaborative arrangement between the Public Health Sciences and the Laboratory Divisions at the International Centre for Diarrhoeal Diseases Research, Bangladesh (ICDDR,B) and the Departments of International Health and Allergy and Immunology the Johns Hopkins University, Baltimore, USA.

Budget Justification:

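### Infant safety is a primary question, but the only between-group analysis named is a test of difference, which says little about safety for reactions with control rates of about 10% or lower

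*Protocol*

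**What the plan says.** Under Primary Objectives, the single primary objective asks whether maternally derived antibody "influences the immunogenicity and safety of glycoprotein conjugate pneumococcal vaccine when given to infants during routine immunization". Appendix 2 carries this through as "Primary: 1b Safety", with percent "reaction rates" as the variable and chi-square as the analysis.

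The Data analysis section names the test twice. In general, "The Chi Square or Fisher's exact test will be used to compare proportions between groups". For safety in particular, "Proportions with adverse events and proportions seroconverting will be compared using chi-square tests".

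The Sample size estimate section works from antibody titers: "A sample size of 63 in each group will allow us to detect a difference of 50% in the final geometric mean titers". After allowance for 30% non-completion, "90 subjects will need to be enrolled in each group, for a project total of 180 mother-infant pairs". The same section gives power for colonization and for correlation coefficients, but none for reactions. Under Policy Implications, the protocol says that "a direct comparison of safety and immunogenicity is needed to allow planning for further studies".

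**The concern.** A chi-square or Fisher test asks whether there is evidence of a difference. It does not say how large an excess of reactions in infants of immunized mothers remains compatible with the data, and that is what a reader needs from a primary safety question. The protocol names this test in both the text and the summary table, so it has fixed the form of the safety analysis and not merely left it open.

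The group size was chosen for a twofold difference in titer. Whether it is also adequate for reactions depends on how common they are, and the protocol gives neither an expected rate nor a detectable difference. If the reactions of interest are uncommon, a real excess would usually give a non-significant result. The planned output would not reveal how little that result excludes, although later studies are to be planned on this comparison.

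**Working it through.** **Inputs from the protocol.** 63 evaluable and 90 enrolled per group, alpha 0.05, power 80% (Sample size estimate); mean log10 titers 0.559 and 0.258, SD 0.601 (Appendix 3). The 2x2 chi-square test is taken as two-sided. Group 1 is the control group and group 2 the maternal pneumococcal group (Appendix 1).

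**Inputs assumed.** Reaction rates, because the protocol gives none. A range is shown.

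**Step 1: the plan's own figure.** n = 2(1.96 + 0.842)² × 0.601² / 0.301² = 62.6, so 63 per group. Power at 63 is 0.803, matching Appendix 3. 63 / 0.70 = 90. The stated sample size reproduces, and it uses titers only.

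**Step 2: power for 10% v 20% by normal approximation.** With mean rate 0.15,

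z = [0.10√n − 1.96√(2 × 0.15 × 0.85)] / √(0.10 × 0.90 + 0.20 × 0.80)

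- n = 63: (0.794 − 0.990) / 0.5 = −0.392, power 0.348
- n = 90: (0.949 − 0.990) / 0.5 = −0.082, power 0.467

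**Step 3: exact check.** All outcomes of two binomials were enumerated, and the probability of those with an uncorrected Pearson chi-square above 3.841 was summed.

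| Assumed rates (group 1 v group 2) | Power, n = 63 | Power, n = 90 | Missed, n = 63 / n = 90 |
|---|---|---|---|
| 2% v 6% | 0.186 | 0.250 | 81% / 75% |
| 5% v 10% | 0.184 | 0.240 | 82% / 76% |
| 10% v 20% | 0.342 | 0.469 | 66% / 53% |
| 15% v 30% | 0.52 | 0.68 | 48% / 32% |
| 20% v 40% | 0.70 | 0.84 | 30% / 16% |
| 25% v 50% | 0.84 | 0.94 | 16% / 6% |

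For 10% v 20%, Fisher's exact test has power 0.264 (n = 63) and 0.397 (n = 90), so the alternative test that the protocol allows does not help.

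**Step 4: what is detectable.** From an assumed 10%, exact power first reaches about 80% at a rate of 29.5% (n = 63) or about 26% (n = 90). By the approximation, 80% power for 10% v 20% needs 199 per group.

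**Step 5: what an interval would show.**

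- With 10% observed in both groups, the 95% half-width is 1.96√(2 × 0.10 × 0.90 / n): 10.5 percentage points at n = 63 and 8.8 at n = 90. An excess of about 9 to 10 points would not be excluded.
- With no events in a group, the exact two-sided 95% upper limit is 1 − 0.025^(1/n): 5.7% at n = 63 and 4.0% at n = 90.

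**The case against.** **The trial is not blind to common reactions.** A reader might infer that any doubling would usually be missed. The table shows otherwise: from 15% a doubling is already found more often than missed, and from 20% or 25% power is 70% to 94%. This stands and limits the point to control rates of about 10% or lower.

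**The protocol never says that non-significance means safe.** This also stands. A reader might infer that the trial intends to declare safety from p > 0.05, but no passage says so, and Policy Implications promises only additional safety information. What remains is that the named analysis offers nothing better to conclude from.

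**Titers are the defined primary outcome measures, so sizing on them is legitimate.** Agreed; a reader should not infer that the sample size is wrong. The gap is that nothing is said about what this size can detect for the other half of the primary objective.

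**63 is pessimistic for safety.** It is the number expected to complete. Reaction cards begin with the first infant dose, and the previous study had 79% completion. The true number per dose probably lies between 63 and 90, but at 90 a rise from 10% to 20% is still missed more often than found.

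**Safety is watched in other ways.** Reaction cards after each dose and a monitoring committee protect participants, but they give no between-group estimate.

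**Intervals can be left to the statistical analysis plan.** That is often so, and that plan could add them. Here, though, the protocol itself has named a bare test as the analysis of a primary item.

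**Conclusion.** The point holds in a limited form. For reactions with a control rate of about 10% or lower, a non-significant result from the named test would say little about safety: a rise from 10% to 20% is missed 53% to 66% of the time, and one from 5% to 10% is missed 76% to 82%. For reactions at 20% or above, a doubling would usually be detected.

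These figures rest on assumed reaction rates, two-sided testing at 0.05 and one observation per infant. Counting the three doses as independent would raise power for 10% v 20% to 78% (n = 63) or 90% (n = 90), but the protocol does not plan that, and doses within an infant are correlated.

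This is a weakness in how a primary question will be answered. It is not an error in the sample size or evidence of an intended false safety claim.

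**What to change.** In the Data analysis section and in the Primary 1b row of Appendix 2, make the safety result the infant risk difference, group 2 minus group 1, with a two-sided 95% confidence interval for fever, local reactions and systemic reactions after each dose. Give exact limits for rare or zero events. State the conclusion by the upper limit, that is, the excess in percentage points that the data exclude, and not by p > 0.05. The tests may stay as a supplement.

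Add one sentence to the Sample size estimate section saying what is detectable. For example, from an assumed 10%, 80% power is reached for a rise to about 26% with 90 infants per group or 29.5% with 63.

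The cost is wording and a few intervals on data already being collected, with no extra participants or visits. The downside is a more modest safety claim.
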